The objective of this study is to demonstrate the performance and intended use of each of the Alinity s investigational assays in a donor screening environment using clinical samples to evaluate assay performance characteristics. A comparison of assay performance will be done versus the Food and Drug Administration (FDA) licensed assays. The data will be used to support regulatory submissions and/or publications.

III. Study Design

A. Overview

Protocol directed testing will be performed at a minimum of 3 testing sites, to evaluate system reproducibility, specificity and sensitivity. For specificity, one of the sites that test specimens from whole blood donor collections will also test specimens from plasmapheresis collections. Specimens will be provided by clinical sites or by Abbott. In addition, panels will be provided by Abbott. A minimum of 3 lots of each of the Alinity s investigational assay reagents, calibrators and controls will be used throughout the study.

The testing or collection sites will provide random donor specimens that are collected as part of the routine blood or plasma donation process to evaluate specificity of each assay. A minimum of 15,000 random donor specimens are needed for the Anti-HCV, HBsAg and HIV Ag/Ab Combo assays collected across a minimum of three whole blood donor centers and one plasmapheresis center. A minimum of 15,000 random donor specimens are needed for the Anti-HBc, HTLV I/II and Chagas assays collected across a minimum of three whole blood donor centers. Each donor specimen may be tested on one or more assays, therefore specimens may be obtained from approximately 23,000 to 90,000 blood donors depending on the number of assays tested on each donor sample. At the time of the blood donation, the donor will be informed that the donor center may use their donation for research studies. Donors will be provided an information sheet explaining this process. The donor may also be asked to return and participate in a follow-up blood collection based on results obtained. The donor will sign a

Confidential Information

This material is the property of Abbott Laboratories and must not be disclosed or used, except as authorized in writing by Abbott Laboratories.

Page 5 of 34

separate research consent form for the follow-up blood collection and have approximately 20 to 60 mLs of blood drawn for testing.

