Specimens should be shipped to Abbott Laboratories for additional testing or to a reference laboratory for supplemental testing as directed by the Abbott monitor. Store the specimens at -20 °C or below and ship overnight on dry ice. When shipped, specimens must be packaged and labeled in compliance with

Confidential Information

This material is the property of Abbott Laboratories and must not be disclosed or used, except as authorized in writing by Abbott Laboratories.

applicable state, federal, and international regulations governing the transport of clinical specimens and infectious substances.

A specimen may be removed from the study if the sample is found unacceptable for testing (e.g. inappropriate handling prior to testing, inadequate volume), or for other assignable causes. The reason for removal must be documented on an Incident CRF. Specimens removed from the study may need to be replaced, if deemed necessary by the Abbott monitor, to meet requirements for the minimum number of specimens.

B. General Study Procedures

1. Assay and/or System Configuration

The investigational Alinity s software is installed onto the Alinity s System at the time of instrument installation. The monitor will provide instructions on software configurations needed to start the study.

2. Instrument System General Procedures

Maintenance procedures are to be performed as instructed in the Investigational Alinity s System Operations Manual. Reports for maintenance and any documentation for component replacements that occurred during the study should be filed in study records.

The on-board inventory of the Alinity s System supplies and reagents will be checked daily. Load consumables and update inventory as necessary.

Refer to the Investigational Alinity s System Operations Manual.

3. Assay Calibration

Each Alinity s blood screening assay will be calibrated as described in the Alinity s Assay Clinical Brochure and the Alinity s Calibrator Clinical Brochure. The calibrator lot number and expiration date information will be read from barcodes when the material is tested on the instrument system. Refer to Calibration Procedures Section of the Alinity s System Operations Manual.

Calibration is to be performed for each investigational reagent lot. Print or transfer electronic report of the calibration and control results for each reagent lot tested. Refer to the Alinity s Assay Clinical Brochure and Alinity s Calibrator Clinical Brochure for frequency of calibration.

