Each of the donor collection sites will provide specimens from random donors representing unique individuals for a total of 15,000 donor specimens for each assay. Whole blood donor specimens will be provided by a minimum of three donor collection sites and one site will provide specimens from plasmapheresis donors for HBsAg, anti-HCV, and HIV Ag/Ab Combo assays. Each testing site will test a portion of the whole blood donor specimens with a distribution of testing across a minimum of three Alinity s reagent, calibrator, and control lots as instructed by the monitor. The testing sites for Alinity s and PRISM may be different. The testing of the plasmapheresis specimens will be distributed across three Alinity s reagent, calibrator, and control lots. The results for the corresponding PRISM comparator assay and NAT assay, as applicable will be provided to Abbott for each donor specimen. Testing of any follow-up donor specimens will be done using the procedure below for the investigational Alinity s assay, comparator assay and supplemental testing as needed.

Approximately 7,600 specimens provided by Abbott will be distributed across the clinical testing sites. Specimens will be tested across a minimum of three lots of Alinity s assay reagents, calibrators and controls. Each site may test approximately 2,500 specimens depending on the total number of clinical sites and representing similar distribution across assay and specimen categories. In addition, the specimens will be tested on the corresponding PRISM comparator method at a minimum of one clinical site. The Abbott monitor will provide the details of which specimens to test for each assay, as well as the reagent/calibrator/control lot combination.

Note: After testing of a specimen, any remaining specimen volume must be retained frozen. The Abbott monitor may request certain procedures or additional testing to be performed for troubleshooting purposes. The additional testing may require various procedures to be repeated.

Note: Specimens should be tested on the same freeze thaw cycle for the Alinity s assay and the comparator method. If the sample has been tested or retested on a subsequent freeze thaw cycle, the event should be documented on an Incident Report form.

Procedure

- 1) Test each Alinity s assay quality control, if daily Alinity s quality controls have not been already tested and assessed for validity.

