The statistical analysis output along with a listing containing each observation collected for this study will be completed. The listing will be printed for data included in the analysis and excluded from the analysis. The excluded listing will include the reasons for exclusion. A summary of the usage of every test result will also be completed, together with the final analysis results, to ensure that there is no data point missing or misplaced in the analysis.

There is no plan to perform interim analyses that evaluate interim data against acceptance criteria. However, interim data monitoring will be conducted to ensure data meets validity criteria and minimum sample size requirements.

B. Statistical Analysis Description

Confidential Information

This material is the property of Abbott Laboratories and must not be disclosed or used, except as authorized in writing by Abbott Laboratories.

Page 24 of 34

1. Reproducibility

a. Study Design

Assay reproducibility will be determined by testing controls and members of a panel at a minimum of three sites with one instrument using a minimum of 3 lots of each Alinity s blood screening assay reagents, calibrators, and controls.

b. Analysis Variables

The analysis variable is Alinity s assay S/CO values for all panel members and controls.

c. Statistical Analysis Method

The analysis method is based on CLSI EP15-A2E. The reproducibility panel members and the Negative and Positive controls will be tested twice a day for a minimum of 5 days per reagent lot (minimum 3 lots) and site (minimum 3 sites). Within each run, each panel member/control will be tested in two aliquots and two replicates will be assayed per aliquot, resulting in four results per sample.

Overall Analysis

Data from all sites and reagent lots for each reproducibility panel/control member will be used for the reproducibility analysis. The following individual variance components will be estimated: within-run, between-run, between-day, between-lot, between-site, and lot-site interaction. The within-laboratory variance is defined as the summation of within-run, between-run, and between-day variance components. The overall assay variability is defined as the summation of within-run, between-run, between-day, between-lot, between-site, and lot-site interaction variance components. The estimates of the mean S/CO, standard deviation (SD) and %CV will be calculated.

By Site Analysis

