Sensitivity can be also calculated as the proportion of repeatedly reactive (RR) specimens with positive status from specimens with positive status and nonreactive (NR) specimens with indeterminate status:

$$\text{Sensitivity} = A / (A + D + E) \times 100\%$$

A two-sided 95% confidence interval for overall sensitivity will be calculated using the exact method based on the binomial distributions.

All sensitivity calculations described above will also be done for the comparator assay.

d. Sample Size

Sample size for specificity is maximum of 15,000 and calculated based on the minimum power of 80% and $\alpha \leq 0.05$.

Sample size for sensitivity is not determined using statistical power calculations. Sample size is determined by the number of available specimens.

e. Level of Significance/Confidence Statement

Two-sided 95% confidence interval (CI) will be provided.

Confidential Information

This material is the property of Abbott Laboratories and must not be disclosed or used, except as authorized in writing by Abbott Laboratories.

f. Data Handling Convention

All results from this testing that are performed according to the protocol and not excluded will be eligible for analysis. Reasons for any exclusion will be captured in the database.

X. Conduct of the Study

A. Responsibilities for Conduct of the Study

- 1) The investigator will have written and dated approval/favorable opinion from the [Institutional Review Board (IRB) or Independent Ethics Committee (IEC)] for the protocol and other documents as specified by the [IRB/IEC] before initiating the study. In some cases, the [IRB/IEC] may provide an expedited or exception review.
- 2) The investigator is responsible for reporting to the [IRB/IEC] and obtaining the necessary approvals from his/her site administration.
- 3) Abbott Laboratories will not initiate the study until the required pre-study documents are received from the site. Pre-study documents are aligned with GCP requirements and a detailed listing of the required pre-study documents will be provided to the investigator by the Abbott monitor.
- 4) The investigator will perform the study in accordance with GCP. The Abbott monitor will provide the investigator with the GCP-aligned list of investigator requirements.
- 5) The Abbott monitor will provide the investigator with the Guidance for Industry Investigator Responsibilities – Protecting the Rights, Safety, and Welfare of Study Subjects (October 2009) for reference.

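### Does calling 15,000 a maximum, with no inputs given for the 80% power, undermine the specificity sample size?

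*Combined protocol and SAP*

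**What the plan says.** The only statistical justification for the specificity sample size is one sentence in IX.B.2.d: "Sample size for specificity is maximum of 15,000 and calculated based on the minimum power of 80" per cent, followed by alpha at or below 0.05. No other input is given.

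The design section, III.A, speaks of a floor twice:
- "A minimum of 15,000 random donor specimens are needed for the Anti-HCV, HBsAg and HIV Ag/Ab Combo assays"
- "A minimum of 15,000 random donor specimens are needed for the Anti-HBc, HTLV I/II and Chagas assays"

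Together these cover all six screening assays. VI.C.2 describes the donors as "representing unique individuals for a total of 15,000 donor specimens for each assay". The table in VI.A.2 divides this into 12,000 whole blood plus 3,000 plasmapheresis donors for three assays, and 15,000 whole blood donors for the other three.

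Two general rules also assume a floor. VI.A.3 allows removed specimens to be replaced "to meet requirements for the minimum number of specimens", and IX.A says that "interim data monitoring will be conducted to ensure data meets validity criteria and minimum sample size requirements".

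For the analysis, IX.B.2.c plans specificity as a proportion with an exact binomial interval, and IX.B.2.e adds: "Two-sided 95% confidence interval (CI) will be provided". IX.A mentions acceptance criteria only to rule out interim looks: "There is no plan to perform interim analyses that evaluate interim data against acceptance criteria".

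**The concern.** Two things look wrong on a first reading.

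First, a maximum and a minimum of the same number appear to contradict each other. A ceiling on the number of donors cannot guarantee a floor on power. If a site or monitor took IX.B.2.d literally, fewer than 15,000 donors would satisfy the statistical section while breaching III.A.

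Second, a power figure means something only relative to a hypothesis. The text does not say what specificity is to be ruled out, what specificity is expected, whether the comparison is with a fixed value or with the licensed comparator, whether alpha is one- or two-sided, or which of the two specificity definitions in IX.B.2.c is powered. At stake would be the support for the study's largest testing commitment, in a file intended for regulatory submissions.

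**Working it through.** **Step 1. How many donors are to be tested?**

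| Place | What it fixes |
|---|---|
| III.A | at least 15,000, all six assays |
| VI.A.2 table | 12,000 + 3,000 = 15,000 (HIV Ag/Ab Combo, HBsAg, Anti-HCV); 15,000 (HTLV I/II, Anti-HBc, Chagas) |
| VI.C.2 | 15,000 in total for each assay |
| IX.B.2.d | 15,000, called a maximum |

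The number is the same everywhere; only the adjective in IX.B.2.d differs. That sentence covers six assays and is written entirely in bounds: an upper bound on size, a lower bound on power and an upper bound on alpha. This fits a summary of several per-assay calculations whose largest result was 15,000. Using that largest size as the floor for every assay agrees with III.A. The text does not say that this is what was meant.

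**Step 2. Can the plan's figure be reproduced?**

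It cannot, because the inputs are missing. A range check needs assumed values; p0 (specificity to be ruled out) and p1 (true specificity) below are all assumptions.

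One-sample normal approximation for 80% power:

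n = [z(1−α)·√(p0(1−p0)) + z(0.80)·√(p1(1−p1))]² / (p1−p0)²

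With p0 = 0.998, p1 = 0.999 and one-sided α = 0.025: (1.960 × 0.04468 + 0.842 × 0.03161)² / 0.001² ≈ 13,034. At one-sided 0.05 the result is 10,018. With p0 = 0.999 and p1 = 0.9995 the results are 26,091 and 20,053.

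Non-inferiority to the comparator, two independent samples, both at 99.9%, margin 0.1 point: n per assay = (1.960 + 0.842)² × 2 × 0.999 × 0.001 / 0.001² ≈ 15,683, or 12,353 at one-sided 0.05. The same donors are tested on both systems, so this is only a rough guide.

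Plausible inputs therefore give sizes on both sides of 15,000.

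**Step 3. Exact power at n = 15,000 under assumed criteria.**

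Let c be the largest false-positive count with P(X ≤ c | 15,000, 1−p0) ≤ α. Power is P(X ≤ c | 15,000, 1−p1).

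| p0 | p1 | c (0.025 / 0.05) | Power (0.025 / 0.05) |
|---|---|---|---|
| 99.5% | 99.7% | 58 / 60 | 97.4% / 98.7% |
| 99.8% | 99.9% | 19 / 20 | 87.5% / 91.7% |
| 99.9% | 99.95% | 7 / 8 | 52.5% / 66.2% |
| 99.8% | 99.85% | 19 / 20 | 27.0% / 34.7% |

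The stated 80% holds for some pairs and not for others. Nothing in the documents selects a pair, so the claim is unverified, not wrong.

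**Step 4. What the planned analysis delivers whatever the inputs were.**

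Exact (Clopper-Pearson) 95% intervals at 15,000 donors, taking all as negative in final status:

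| False positives | Specificity | 95% CI |
|---|---|---|
| 30 | 99.80% | 99.72% to 99.87% |
| 15 | 99.90% | 99.84% to 99.94% |
| 7 | 99.95% | 99.90% to 99.98% |

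These intervals need no null value, margin or sidedness for a test. They are what IX.B.2.c and IX.B.2.e commit to reporting.

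**The case for a change.** The strongest case for a change is that the data will support regulatory submissions, that this one sentence is the only statistical reason given for 15,000 donors on each of six assays (IX.B.2.d itself says sensitivity was not powered), and that Step 3 shows the omitted inputs decide whether the 80% is true. Putting it right would take a few words and no extra donors.

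Part of this stands. The wording does conflict if read literally, and a reader cannot recompute the power. Three points limit its weight.

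- A literal ceiling has no practical route to harm. Stopping at 12,000 would lower power from 87.5% to 77.2% in the 99.9% against 99.8% example (one-sided 0.025), but III.A forbids stopping there. No interim look at results against criteria is planned, so the donor count cannot be steered by results through that route.
- The inputs may exist outside this document. The outlier rule in IX.B.1.g relies on an imprecision product requirement whose value is not given either, so the protocol does refer to numerical requirements held elsewhere. That supports saying the inputs are not stated here, and no more.
- Tying the power to a lower confidence limit exceeding a set criterion would add a success rule that the plan does not contain. The stated objective includes comparison with licensed assays, so a one-sample criterion is not even the obvious basis.

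**Conclusion.** No change follows. The word maximum is a clerical looseness that three other places in the protocol resolve, and the missing power inputs are a reporting gap on which no planned result depends. Following the plan as written yields 15,000 donors per assay and exact 95% intervals about 0.1 percentage point wide near 99.9% specificity (99.94 − 99.84 = 0.10). Testing somewhat more than 15,000, as III.A allows, would only narrow them.

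This rests on reading 15,000 as the number to be collected, on the interval analysis in IX.B.2.c being the one reported, and on nearly all donors having negative final status. The power range of 27.0% to 98.7% rests wholly on assumed criteria and is not evidence that the study is too small. If the document were reopened for another reason, aligning the adjective with III.A would be a courtesy to the reader; it would alter no specimen number, estimate or conclusion.

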Appendix 1: Scientific Amendment

Amendment No: 4

Summary of Changes

The following change incorporated in Protocol No. 09DY-02-14U01-03, Version 5, dated April 18, 2018 is referenced from Version 4, dated October 13, 2017.

1. Change: Section III. C. Study Design, General Schedule of Events, change to “The study will take approximately 5-10 months to complete.”

Detailed Description of Changes

Change 1 (Scientific Change)

- Change: Section III. C. Study Design, General Schedule of Events, change “The study will take approximately 5 months to complete.” to “The study will take approximately 5-10 months to complete.”
- Reason: The change is made to ensure the duration of study reflects the actual duration.
- Justification: Due to the change in strategy for execution of the protocol, the study duration is extended for sites remaining open for Chagas testing. A Protocol Impact Assessment form was completed to assess the impact of clinical study testing. There is no impact to the clinical study.

End of Document

Confidential Information

This material is the property of Abbott Laboratories and must not be disclosed or used, except as authorized in writing by Abbott Laboratories.

Page 34 of 34
